What are the known safety concerns of the treatment(s), and are the concerns different for the proposed repurposed indication? This study will investigate the use of antibiotics and possibly other medications (eg. promotility, bile sequestrants, anti-diarrheals) for SSc SIBO treatment. For all antibiotics, hypersensitivity reactions such as exfoliative dermatitis, rash, urticaria, flushing, angioneurotic edema, pruritus, and anaphylaxis are a concern. Prolonged use may result in fungal or bacterial super-infection, including *C. difficile*-associated diarrhea and pseudomembranous colitis. Cholestyramine resin, which may be one of the drugs selected for use, should be used with caution in patients with triglyceride levels 250-299 mg/dL. Chronic use may be associated with bleeding problems (especially in high doses. Cholestyramine (especially high doses or long-term therapy) may decrease the absorption of folic acid, calcium, fat-soluble vitamins (vitamins A, D, E, and K), and iron. However, antibiotics and drugs such as cholestyramine are already in use for SIBO, although not in a standardized fashion, so the risks are not increased in this proposal. The use of certain promotility drugs is associated with a prolonged QT interval.

THE PILOT PROJECT

Objectives: To determine the feasibility of the full project. This will be a trial with 3 months of recruitment and 6 months of follow up for each case.

Specific Aims:

1. Determine if ethics committees perceive any major issues regarding the ultimate trial
2. Determine if the sites are approaching all eligible patients with study and offering consent forms.
3. Determine the signing rate of consent.
4. Determine patient adherence to web access for questionnaires.

Pragmatic, multicentre, cluster, cohort randomised controlled treat-to-target trial for treatment of small intestinal bacterial overgrowth in systemic sclerosis (SSc) – A Pilot Project

5. Assess our method for detecting eligible cases from web questionnaires.
6. Assess whether physician notifications are being sent out quickly after detecting eligible cases.
7. Assess the timeliness and completeness of physician receipt of notification of patient eligibility.
8. Assess physician adherence to treatment protocol:
 - a. how soon protocol patients are brought in to see doctor after receipt of notice.
 - b. does doctor record what he does accurately.
 - c. does he/she schedule return visits according to protocol.

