Website Questionnaires: Subjects will access and fill in the GSS questionnaire which will be used both for screening for SIBO and for assessment of improvement with treatment. If the score of the GSS is ≥ 5 then the UCLA GIT and PROMIS GI questionnaires will also be triggered. (Appendix 4 – Questionnaires) They will be sent the link to the questionnaires via email from the central study coordinator. In this pilot, we will only screen subjects for 3 months total so the questionnaires will be filled in once a month for those 3 months. This will allow us to better assess the use of the website over a short period of time. Subjects will be notified immediately after consent is signed and thereafter once a month by email that they should fill in the questionnaire. A link will be provided. If the questionnaire is not filled out within 5 days an automatic repeat email will be sent out. We will repeat this every 5 days for a total of 3

Pragmatic, multicentre, cluster, cohort randomised controlled treat-to-target trial for treatment of small intestinal bacterial overgrowth in systemic sclerosis (SSc) – A Pilot Project

additional reminders. If there is no response after that the site coordinator will be informed and asked to phone the subject to determine and record the reason for the non-response and if the subject no longer wishes to be in the study they will be withdrawn.

Notification of Doctor of Eligible Case: If a score on the GSS is ≥ 5 , the computer will send an automatic notice to the office of the doctor and to the doctor him/herself telling them of this. The email notification will be repeated in 5 days to be sure that it has not been missed, and the provider will be asked to verify that it was received.

First Appointments: Upon receipt of the notice, the protocol doctors will be expected to make an appointment within the timeframe outline in the protocol. Standard care doctors, who will not know the details of this protocol, will decide on their own if and when to see the patient. Upon receipt of this notice the secretaries or clerks at the site will be asked to insert a treatment sheet (Appendix 5 – Treatment Sheet) in the doctor's chart. This sheet will be used to assess the timeliness of the first visit after notification, about the adherence of protocol doctors to protocol treatment and the types of medications and general pattern of treatment of the standard of care doctors.

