Subsequent Appointments: The timing of subsequent appointments will be left to the discretion of the doctors but the protocol doctors will be expected to adhere to the protocol for follow up frequency and intervals. The treatment sheets will assess adherence. At each protocol visit the patient will fill out the GSS in the office as the doctor will use the score to determine success of treatment rather than relying simply on history. This is outlined in detail in the treatment protocol.

Recruitment and follow-up period: Patients will be recruited over a period of 3 months and followed up for 6 months. The total duration of the study will thus be 9 months. However, the protocol doctors will be asked to try to continue to adhere to the protocol. If there are no major changes in the protocol based on this pilot, all the patients enrolled in these 3 months may be rolled into the larger full study. This will be decided after the pilot data has been fully assessed.

Safety Monitoring: The treatment sheets will have fields to record any suspected side effects of treatment and the physicians will record this. A Data Monitoring and Safety Board (DSMB) will be established before the start of the pilot. We will request that a copy of all treatment sheets be faxed or emailed to the coordinating site after each visit. These will be forwarded to the DSMB members. If any member detects a serious side effect that they feel should lead to a change in protocol an immediate teleconference of the DSMB will be arranged.

Chart Audit: To determine if there is a disagreement between the treatment questionnaires and what the doctors actually did, we will perform a chart audit of a sample of charts. Permission to do this will be included in the consent forms. We will audit 30 % of charts randomly selected from each doctor. The audits will be of all relevant visits over the study period. We will ask to have the relevant pages from these charts faxed to us. We will find non-English speaking volunteers from the translation service at the central coordinating hospital to help fill out data extraction forms (Appendix 6 – Data Extraction Sheet) for the chart review of non-English speaking centers. The study coordinator will perform the audit.

Data Analyses: Each of the aims will be assessed. Statistics will be essentially descriptive. The success of the pilot will not depend on one global assessment. As individual elements of the

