If Not Successful: We will modify the sample size calculations and power of the full study

Pragmatic, multicentre, cluster, cohort randomised controlled treat-to-target trial for treatment of small intestinal bacterial overgrowth in systemic sclerosis (SSc) – A Pilot Project

6. Assess whether physician notifications are being sent out quickly after detecting eligible cases.

Success: All notifications should go out immediately after scoring GSS by computer.

If Not Successful: Address computer program.

7. Assess the timeliness and completeness of physician receipt of notification of patient eligibility.

Success: Receipt of notification by email should be within one day in all cases.

If Not Successful: Address computer program. Make sure correct email addresses.

8. Assess physician adherence to treatment protocol:

a. How soon protocol patients are brought in to see doctor after receipt of notice.

Success: The window is in the treatment protocol. 90% of visits should be within the window.

If Not Successful: Speak to physicians and see what the issues are that delay appointments. Determine if something can be done to protocol to address this.

b. Does doctor record what he does accurately.

Success: This will be assessed by chart audit. We expect the chart to reflect the answers on the treatment forms on 90% of all filled in fields on each form.

If Not Successful: We will discuss with the physicians why there was a difference between charts and forms and determine if the protocol can be changed to enhance the adequacy of completion of the forms.

c. Does he/she schedule return visits according to protocol.

Success: This will be assessed by chart audit. 90% of visits should be within the window.

If Not Successful: Speak to physicians and see what the issues are that delay appointments. Determine if something can be done to protocol to address this.

d. Does he/she use in office questionnaires for treat to target.

Success: Use chart audit. At >90% of protocol visits the questionnaires should be filled out and found in chart. We also expect to find notes suggesting that physician treatment decisions take into account the score on the GSS.

If Not Successful: Speak to physicians and see why questionnaires not being used appropriately and determine if protocol changes can be made.

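### Item 8a scores timeliness over visits, so a notified protocol patient who is never seen cannot count as a miss; item 8c shares the weakness in a more ambiguous form

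*Protocol*

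**What the plan says.** In the Protocol, The Pilot Project, Data Analyses, item 8 sets success rules for physician adherence at the treatment-protocol sites.

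- **Item 8a, question:** "How soon protocol patients are brought in to see doctor after receipt of notice".
- **Item 8a, rule:** "Success: The window is in the treatment protocol. 90% of visits should be within the window".
- **Item 8c, question:** "Does he/she schedule return visits according to protocol".
- **Item 8c, rule:** "This will be assessed by chart audit. 90% of visits should be within the window".

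If either item fails, the planned response is to ask the physicians what holds appointments up and whether the protocol can be adapted.

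Three other places bear on who is counted. The First Appointments paragraph says "Upon receipt of this notice the secretaries or clerks at the site will be asked to insert a treatment sheet", and that sheet is meant to show how timely the first visit was. The Safety Monitoring paragraph has copies of the sheets sent to the coordinating site after each visit. The Chart Audit paragraph samples 30% of each doctor's charts and adds: "The audits will be of all relevant visits over the study period".

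**The concern.** The question in 8a is put per notified patient, while its rule is put per visit. The two agree only if every notified patient is seen. A late visit counts against the site. A patient who is never brought in generates no visit and, on the wording, counts against nobody. Item 8c has the same structure: a return visit that was due and never arranged is not obviously one of the visits being scored.

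Getting flagged patients in, and back again, is how the treat-to-target strategy is delivered. The full trial plans to follow each patient from the moment the physician is notified, so a flagged patient never seen at a protocol site would stay in follow-up without having received the strategy. If item 8a is scored as met while many patients are in that position, the planned conversation with physicians is not triggered and the weakness may carry into the full trial.

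**Working it through.** **Nothing to reproduce.** The 90% is a chosen threshold with no derivation, and the protocol describes the statistics as essentially descriptive. The check is therefore denominator arithmetic and a comparison of items.

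**Inputs.** The 90% threshold per visit comes from items 8a and 8c. The share of notified patients who are seen, s, is not given; I assume 50% to 100%. The number of notified protocol-site patients is not given either; I use 20 for illustration.

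**Formula.** If exactly 90% of visits fall in the window, the in-window share of notified patients is 0.90 × s.

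| Share seen, s | In-window share of visits | In-window share of notified patients |
|---|---|---|
| 100% | 90% | 90% |
| 90% | 90% | 81% |
| 80% | 90% | 72% |
| 70% | 90% | 63% |
| 60% | 90% | 54% |
| 50% | 90% | 45% |

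Read literally, the rule is met in every row. The same arithmetic applies to 8c if s is the share of due return visits that took place.

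**Whole-number examples (assumed counts).**
- 20 notified, 12 seen, 11 in the window: 11/12 = 91.7%, met; per notified patient 11/20 = 55%.
- 20 notified, 10 seen, 9 in the window: 9/10 = 90%, met; per notified patient 9/20 = 45%.

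**How easily the rule is met.** With 12 visits, at least 11 must be in the window. If each visit is on time with probability 0.95 (assumed), the chance is 12 × 0.95^11 × 0.05 + 0.95^12 = 0.341 + 0.540 = 0.88. Counted over all 20 notified patients, 90% could not be reached: with 12 seen, the most possible is 12/20 = 60%.

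**Does another item catch the unseen patient?**
- Items 6 and 7 stop at sending and receipt of the notice.
- Item 8d is again counted over protocol visits.
- Item 8f expects at least 80% adherence to the algorithm by chart audit. It states no denominator and no rule for patients never seen.

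**How the protocol handles the same problem elsewhere.** Item 4 has two parts: at least 70% of patients answer the first questionnaires, and at least 90% of those who answer do so within 10 days. Item 2 takes all yearly INSYNC patients as its base. Item 8a has the timeliness part but no completeness part.

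**The case against.** **Visits may mean visits expected.** Neither item says it counts only visits that took place. If expected visits are meant, a missing visit is not in the window and the problem disappears. This reading is plausible for 8c, which asks about scheduling. It is weaker for 8a: nothing in the item states it, and sheets are returned only after a visit. The point stands for 8a on its wording; for 8c it is a request to settle an ambiguity.

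**The detail may sit elsewhere.** Exact denominators are often left to an analysis plan, and the treatment protocol and appendices are not shown. But the rule and its unit are fixed in this protocol, and the unit does not match the question. That is a fault of the stated rule, not an omission.

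**Unseen patients are not wholly hidden.** A reader might infer that they leave no trace. The documents do not support that. The sheet is to be placed in the chart once the notice arrives, so an unused one can be found if that chart falls in the 30% sample. A descriptive account of aim 8a may also show them, and 8f may pick up skipped return visits. These are partial safeguards, and none sets a threshold for the share of notified patients seen.

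**Physicians should not answer for everything.** Counting from the moment a notice is sent would charge e-mail failures, which belong to item 7, to the doctor. Counting every return visit that did not happen would charge patient no-shows to a doctor who scheduled correctly. Both objections are sound and shape the fix.

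**Conclusion.** The point holds for item 8a: as worded, its success rule can be met while a substantial share of notified protocol patients is never seen, and no other item sets a limit on that share. A result that just meets 90% of visits corresponds to 45% to 81% of notified patients seen on time when 50% to 90% are seen. These figures show what the rule would tolerate and do not forecast what will happen, since the documents give no expected share.

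For item 8c the weakness is the same in form but less certain, because visits due is a natural reading there and 8f is a partial backstop.

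A reader might infer that the pilot as a whole could pass and so declare the intervention deliverable. The protocol does not support this: the Data Analyses section rules out a single overall judgement and assesses each element separately. The finding is limited to how these two items are scored. It does not question the length of the window, which sits in the treatment protocol.

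**What to change.** **Item 8a.** Take as denominator all protocol-site patients whose notice was received by the site. Count a patient with no visit by the end of the existing window as not within it. Require 90% on that basis, and report the share never seen.

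**Item 8c.** Take as denominator all return visits due under the treatment protocol in the audited charts. Count a due visit that was not scheduled within the window as a miss. Report patient no-shows and withdrawals separately, so that the item still measures what the physician did.

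**Cost.** Two or three sentences of protocol wording. The 8a denominator can be built from what the pilot already generates: automatic notices, the provider's verification of receipt, and the sheet inserted on notification. The coordinating site must tabulate received notices against first visits, including patients for whom no sheet came back, and the audit must list due visits as well as those held. That is slightly more tabulation, and the adherence figures may look less favourable. The window and the 90% threshold stay as they are.

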Pragmatic, multicentre, cluster, cohort randomised controlled treat-to-target trial for treatment of small intestinal bacterial overgrowth in systemic sclerosis (SSc) – A Pilot Project

study can each be addressed separately, by making changes to specific parts of the protocol, the success of each element will be as follows:

1. Determine if ethics committees perceive any major issues regarding the ultimate trial.

Success: There will be 10 sites and thus 10 ethics committee responses. Success will be **NO** substantive suggested changes to the protocol.

If Not Successful: **Any** suggestion for a change will be addressed for full trial.

2. Determine if the sites are approaching all yearly INSYNC patients with study and offering consent forms at the time of the visit.

Success: $\geq 80\%$ of yearly INSYNC patients are offered the consent.

If Not Successful: Interview the local research assistants or nurses and see if there seems to be a systemic issue that could be addressed to improve the frequency with which patients are approached.

3. Determine the signing rate of consent within 1 week of the time of the visit.

Success: $\geq 80\%$ acceptance rate by patients.

If Not Successful: Interview the local research assistants or nurses and see if there seems to be a systemic issue that could be addressed to improve the acceptance rate.

4. Determine patient adherence to web access for questionnaires.

Success: $\geq 70\%$ of patients go to website and answer first set of questionnaires. $\geq 90\%$ of those who answer do so within 10 days. For those who do answer first questionnaire, consider them as successes and study participants. For these subjects, do similar assessments for each subsequent questionnaire. Successful retention will be $\geq 80\%$ of those who answered each month will do so at following month.

If Not Successful: We will consider changes to the wording and frequency of reminders.

5. Assess our method for detecting eligible cases from web questionnaires.

Success: We expect that about 25% of cases will show SIBO positive responses (score ≥ 5 on GSS) to the questionnaires at some point over 3 months. In the study of 51 unselected patients with SSc, 22 (43.1%) patients were identified who fulfilled the breath test criteria of SIBO¹⁰. The sensitivity and specificity of GSS of digestive symptoms >5 to predict SIBO 0.909 and 0.862, respectively. In the 51 cases, 19 patients (37%) has scores > 5 .

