Pragmatic, multicentre, cluster, cohort randomised controlled treat-to-target trial for treatment of small intestinal bacterial overgrowth in systemic sclerosis (SSc) – A Pilot Project

e. Does he/she base decisions on these questionnaires?

Success: as above

If Not Successful: as above

f. Does he/she follow algorithm sequentially.

Success: Use chart audit. We expect $\geq 80\%$ adherence to protocol over the 3 months by ≥ 80 of physicians.

If Not Successful: Speak to physicians and see why algorithm not always being followed and determine if protocol changes can be made.

9. For control sites,

a. Record how soon protocol patients are brought in to see doctor after receipt of notice.

Success: No criteria for success. Just observational

If Not Successful: N/A

b. Assess whether the doctor accurately records what he/she does.

Success: This will be assessed by chart audit. We expect the chart to reflect the answers on the treatment forms on 90% of all filled in fields on each form.

If Not Successful: We will discuss with the physicians why there was a difference between charts and forms and determine if the protocol can be changed to enhance the adequacy of completion of the forms.

Pragmatic, multicentre, cluster, cohort randomised controlled treat-to-target trial for treatment of small intestinal bacterial overgrowth in systemic sclerosis (SSc) – A Pilot Project

References:

5. Bassel M, Thombs B, Hudson M, Taillefer D, Canadian Scleroderma Research Group, Baron M. Sociodemographic, Disease, and Symptom Correlates of Fatigue in Systemic Sclerosis: Evidence from 482 Canadian Scleroderma Research Group Registry Patients (abstract). *Canadian Rheumatology Association. Mont Tremblant, QC2008.*

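### Recording accuracy in items 8b and 9b is scored only on filled-in fields, so where the sheet allows blanks, an action in the chart but missing from the form cannot lower the score

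*Protocol*

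**What the plan says.** Under Data Analyses in the Protocol, item 8b (protocol sites) and item 9b (control sites) ask whether the doctor's record of his or her own actions is accurate. Both are settled by chart audit with the same success rule: "We expect the chart to reflect the answers on the treatment forms on 90% of all filled in fields on each form". If the rule is not met, the differences between charts and forms are discussed with the physicians, and changes are considered that would "enhance the adequacy of completion of the forms".

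The Chart Audit section gives the purpose of the exercise: "To determine if there is a disagreement between the treatment questionnaires and what the doctors actually did". It covers a random 30% of each doctor's charts and all relevant visits in them.

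The form being audited is the treatment sheet. According to First Appointments, it is to supply the timing of the first visit, the adherence of protocol doctors, and "the types of medications and general pattern of treatment of the standard of care doctors". Under Safety Monitoring, it also carries the fields for suspected side effects, and copies go to the safety board.

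The other control-site item, 9a, is declared to have "No criteria for success. Just observational".

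**The concern.** A record can be wrong in two ways. The form can state something that the chart does not bear out, or it can omit something that the chart contains. The audit's stated purpose covers both. The success rule takes its denominator from the form's filled-in fields, so it sees only the first kind.

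A site could therefore pass on accuracy while under-recording treatment, and no review of the forms would follow. No other item sets a bar for form completeness. Sites keep their assignment in the full study and pilot patients may be carried into it, so a false pass would take a recording system forward with its omissions untested.

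The exposure is greatest at control sites. There, 9b is the only criterion under item 9, and the sheet is the planned source for describing standard care. At protocol sites, items 8c, 8d and 8f use the chart audit directly, so an omitted action may come to light that way. Control sites have no counterpart.

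**Working it through.** The 90% bar is a chosen threshold and the pilot states no sample size or power, so there is no figure of the plan to reproduce. The check asks how the rule behaves when fields are left blank.

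**Step 1: what the rule counts, field by field.**

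| Form | Chart | Under 8b/9b |
|---|---|---|
| Filled | Agrees | Match |
| Filled | Disagrees or silent | Mismatch |
| Blank | Holds the information | Not counted |
| Blank | Silent | Not counted (rightly) |

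Only the third row is at issue.

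**Step 2: notation.** On an audited form, let F be the number of filled-in fields and B the number left blank although the chart holds the information. Let a be the agreement on the filled fields and c = F / (F + B).

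- Score under the stated rule: aF / F = a. Pass if a ≥ 0.90. The value of c plays no part.
- Score with omissions counted: aF / (F + B) = a × c. Pass if a × c ≥ 0.90, that is, a ≥ 0.90 / c.

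**Step 3: a result that needs no assumed completion rate.** Since a cannot exceed 1, a × c cannot exceed c. Once c is below 0.90, the omission-counting score fails at every a, including a = 1. The stated rule still passes at any a ≥ 0.90.

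**Step 4: agreement needed on filled fields if omissions count.**

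- c = 1: a ≥ 0.90, the same as the stated rule.
- c = 0.95: a ≥ 0.90 / 0.95 = 0.947.
- c = 0.90: a = 1.00.
- c < 0.90: cannot pass.

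**Step 5: illustration.** The protocol gives no c, so these values are assumptions. For a form scored at exactly 90% under the stated rule (a = 0.90):

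| c (assumed) | Correctly recorded, a × c |
|---|---|
| 1.0 | 90% |
| 0.9 | 81% |
| 0.8 | 72% |
| 0.7 | 63% |
| 0.5 | 45% |

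At the extreme, a form with half of the relevant fields filled, all agreeing with the chart, scores 100% as written and 50% with omissions counted.

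**The case against.** The strongest reply is that the gap may be small or absent. The treatment sheet and the data extraction sheet are appendices that are not shown. If the sheet asks for a yes or no on each drug and each side effect, an omitted drug becomes a wrong no, which the rule already counts. This stands, and it limits the point to fields that can be left blank.

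Three stronger readings might be inferred, and the Protocol supports none of them.

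- *That 9b is the only success criterion at control sites.* It is the only one under item 9. Aims 1 to 7 are not confined to protocol sites and set criteria or expectations on ethics review, consent, web response, case detection and notification. None of these tests treatment recording, which is why the control-site argument survives in narrower form.
- *That the measure cannot detect anything its remedy addresses.* The remedy starts from differences between charts and forms, and the rule does detect those on filled fields. Adequate completion can also mean correct completion, not only the absence of blanks. Measure and remedy are mismatched only for omissions.
- *That forms will in fact be incomplete.* Nothing in the Protocol says so.

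It is also fair to say that the pilot is descriptive, that success does not hang on one overall judgement, and that failing 8b or 9b leads only to discussion and possible changes. Copies of all sheets are requested after each visit, so a largely empty sheet would be noticed, though a single omitted drug would not. These points lower the stakes. They do not make the rule measure what the audit is for.

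**Conclusion.** The point holds in limited form. As fixed in 8b and 9b, the rule tests whether what was written on the form is borne out by the chart. It does not test whether what is in the chart reached the form. It can therefore pass a form at 90% regardless of completeness, and it gives a false pass whenever agreement on filled fields is at least 90% but agreement times completeness is below 90%. With more than 10% of the fields that have chart information left blank, that happens even when every filled field is right.

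The conclusion rests on reading the denominator literally and on the sheet allowing at least some blanks. The practical size cannot be derived from the Protocol; the 81% and 63% figures show only the direction and scale under assumed completion rates. This is a stated criterion that falls short of its own purpose, not a detail left to a later document. It is worth correcting, chiefly for the control sites, but it does not endanger the pilot as a whole.

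**What to change.** In items 8b and 9b, replace the denominator with all fields applicable to the audited visit. Count a blank as a mismatch where the chart holds the information, and leave out a blank where the chart is silent too. The 90% bar can stay.

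Alternatively, keep the present 90% agreement rate and add a completeness criterion beside it, for example that 90% of applicable fields with information in the chart are filled in. This is looser: with both bars just met, 0.90 × 0.90 = 81% of those fields are correctly recorded. The choice between the two should be deliberate.

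If the treatment sheet already forces an entry in every field, a sentence saying so would settle the matter.

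The cost is small, since the same charts, forms and auditor are used. The auditor must mark which fields applied at each visit, and the reported accuracy rate may become less favourable.
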